### 4.3.2 Secondary outcomes

Descriptive statistics of MICs with N, mean (s.d.), median (IQR), min, and max will be summarized by mutation Group (inhA mutation, katG mutation, or neither of these mutations). Box plot of MICs by mutation Group with Q1, median, mean, and Q3, histogram to examine possible bimodal distributions, and plot of 95% confidence interval for the mean MICs by mutation Group will be created.

Nonlinear mixed model using SAS procedure NLMIXED will be fit to estimate the decrease of log10 CFU counts per day for the 'early' and 'terminal' phase. If there is no clear bi-phase pattern, linear mixed model using SAS procedure MIXED will be used. All available log10 transformed CFU counts at all time points will be included as a dependent variable, and day of the samples will be included as the primary exploratory variable in the model for each cohort. Note: The analysis for this outcome will be performed for Group 1 and Group 2.

Nonlinear mixed model using SAS procedure NLMIXED will be used to estimate the increase of TTD per day for the 'early' and 'terminal' phase. If there is no clear bi-phase pattern, linear mixed model using SAS procedure MIXED will be used. Log10 transformation may be applied if appropriate. TTD from all time points (excluding results from contaminated samples or re-culture of contaminated samples after addition decontamination) will be included as a dependent variable, and day of the sample will be included as exploratory variable in the model for each cohort.

Additional analyses will be conducted:

- Descriptive statistics of EBA0-2(CFU) with N, mean (s.d.), median (IQR), min, and max for each of the cohorts will be reported. Box plot of EBA0-2(CFU) with Q1, median, mean, and Q3 and plot

with 95% confidence intervals for the mean EBA0-2(CFU) will be created for each cohort. Note: Note: The analysis for this outcome will be performed for Group 1 and Group 2.

- Descriptive statistics of EBA2-7(CFU) with N, mean (s.d.), median (IQR), min, and max for each of the cohorts will be reported. Box plot of EBA2-7(CFU) with Q1, median, mean, and Q3 and plot with 95% confidence intervals for the mean EBA2-7(CFU) will be created for each cohort. Note: The analysis for this outcome will be performed for Group 1 and Group 2.
- Descriptive statistics of EBA0-2(TTD) with N, mean (s.d.), median (IQR), min, and max will be reported by each cohort. Box plot of EBA0-2(TTD) with Q1, median, mean, and Q3 and plot of 95% confidence interval for the mean EBA0-2(TTD) will be created for each cohort.
- Descriptive statistics of EBA2-7(TTD) with N, mean (s.d.), median (IQR), min, and max will be reported by each cohort. Box plot of EBA2-7(TTD) with Q1, median, mean, and Q3 and plot of 95% confidence interval for the mean EBA2-7(TTD) will be created for each cohort.

Note: The analysis of secondary PK endpoints as described in the protocol Section 9.2.2.1 and 9.2.2.3 will be provided in a separate PK analysis plan.

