1.0 HYPOTHESES AND STUDY OBJECTIVES

1.1 Hypotheses

- 1.1.1 In the majority of participants infected with TB with *inhA* mutations, drug concentrations can be achieved that will result in an early bactericidal activity (EBA) measured as the daily fall of \log_{10} colony-forming unit (CFU)/mL sputum over 7 days (EBA₀₋₇ (CFU)) that is at least 50% the EBA₀₋₇ (CFU) of standard-dose isoniazid (INH) when given to participants with drug-sensitive TB (DS-TB).
- 1.1.2 High-dose INH will be well tolerated in a majority of participants.
- 1.1.3** Among participants infected with TB with *katG* mutations (Group 3), the distribution of minimum inhibitory concentrations (MICs) will be wide, but, **nevertheless, INH at a dose of 15 or 20 mg/kg daily will have measurable activity.**

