INH is cheap, widely used, orally bioavailable, safe, and generally free of drug-drug interactions. It has potent EBA and plays an important role in rapidly reducing the bacterial burden and preventing the selection of drug-resistant mutants [7, 13]. Against drug-susceptible strains, INH alone is able to decrease the bacterial burden by 90-95% in the first two days of treatment. Although INH exposures are influenced by the patient's acetylator status, near maximal activity against drug-susceptible strains is observed at the commonly prescribed dose, even in rapid acetylators. INH is a prodrug that is activated by the *M. tuberculosis* catalase-peroxidase encoded by *katG* [6]. The activated drug inhibits the activity of the enoyl-acyl carrier protein reductase (*inhA*) and thereby blocks mycolic acid synthesis [14]. Against susceptible strains of *M. tuberculosis*, the MIC is 0.03-0.06 mcg/mL. Mutations in the *katG* gene may result in partial loss of KatG function, resulting in reduced INH activation and INH MICs of 2 to 8 mcg/mL or, alternatively, complete loss of KatG function, no INH activation, and INH MICs \geq 16 mcg/mL. On the other hand, mutations in *inhA* and the *inhA* promoter region are associated with low-level resistance (MIC 0.2-1 mcg/mL) and cross-resistance with ethionamide. Data on the distribution of INH MICs against clinical DR-TB isolates are sparse [15], but reports suggest *inhA* mutations account for 30-40% of INH-R strains, and as many as 43-75% of MDR-TB strains are susceptible to INH concentrations <5 mcg/mL [16]. Since INH concentrations well above this level are achievable in patients receiving INH in moderately elevated dosages (higher-dose INH), patients infected with low-level-resistant strains may represent a substantial sub-population of DR-TB in which high-dose INH may be effective.

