## 4 Statistical Methods

### 4.1 General Considerations

Baseline characteristics will be summarized by cohorts (by Group and treatment arm) but with no statistical comparisons comparing cohorts.

Categorical data will be summarized using N (%), and continuous data using N, min, Q1, median, Q3, max, and mean (STD) (when appropriate). Nonlinear mixed model using SAS procedure NLMIXED will be used to estimate the decrease of log10 CFU counts per day for the 'early' and 'terminal' phase as well as the increase of TTD per day. If there is no clear bi-phase pattern, linear mixed model using SAS procedure MIXED will be used. For TTD, log10 transformation may be applied if appropriate. Any modifications to outcome measures after the team has seen data collected after entry will be considered as post hoc.

The primary endpoint analysis is defined in Section 4.3.1; however, the secondary modeling approach, which is described in Section 4.3.2, might be more appropriate in case of missing CFU or TTP outcomes at baseline and Day 7.

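### SAP 4.3.2 plots a 95% CI for the arithmetic mean MIC, a poor summary for Group 3 (katG) and one that would depend on coding if many isolates exceed the tested range

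*SAP*

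**What the plan says.** SAP 4.3.2 sets out the MIC summary: "Descriptive statistics of MICs with N, mean (s.d.), median (IQR), min, and max will be summarized by mutation Group". It adds a box plot that shows the mean, a "histogram to examine possible bimodal distributions", and a "plot of 95% confidence interval for the mean MICs by mutation Group will be created". The mutation groups are inhA, katG and neither.

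No scale is named for MIC. Elsewhere the SAP does name one: CFU is analysed as log10 (SAP 3.2), and "For TTD, log10 transformation may be applied if appropriate" (SAP 4.1). SAP 3.2 also has limit rules for those two assays: a CFU count of zero gives a log10 value of zero, and a TTD of 42 days is referred to the site. MIC has no such rule. Protocol 6.3.1 says only that the MIC will be determined, without the concentrations tested.

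The protocol does say what to expect. Section 2.1 gives 0.03 to 0.06 mcg/mL for susceptible strains and 0.2 to 1 for inhA mutants. For katG it describes partial loss of function with "INH MICs of 2 to 8 mcg/mL or, alternatively, complete loss of KatG function", the latter with MICs of 16 mcg/mL or more. Hypothesis 1.1.3 expects that in Group 3 "the distribution of minimum inhibitory concentrations (MICs) will be wide".

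**The concern.** MICs are read at a limited set of concentrations, usually in doubling steps, and behave multiplicatively. From the lowest susceptible value to the open katG category, the background figures differ by a factor of at least 16/0.03, or about 530. The SAP summarises by mutation group, so the within-group spread is what counts. It is twofold for susceptible strains (0.06/0.03), fivefold for inhA (1/0.2) and at least eightfold, with no upper limit, for katG (16/2). Group 3 is therefore where an arithmetic mean with a CI says least, because a few high values dominate it.

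There is also a conditional problem. If some isolates still grow at the highest concentration tested, their MIC is known only to exceed a limit. A mean, an SD and a CI all need a number in that place, and the plan does not say which. At stake is the usefulness and reproducibility of one posted summary of a secondary objective.

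**Working it through.** The documents state no MIC mean, SD or CI, so there is no figure of the plan's own to reproduce. What follows is a sensitivity calculation.

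**From the documents.** Clarification Memo #1 to Version 3.0 expects 40 Group 3 participants under that version (20 in Step 1 only, 20 in Steps 1 and 2). Protocol 2.1 gives the katG values of 2 to 8, or at least 16.

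**Assumed.** On-scale isolates are spread as evenly as possible over 2, 4 and 8. A share p is known only to be at least 16 and is entered as 16, 32 or 64. The CI is the usual t interval, mean ± t(0.975, n−1) × SD/√n; the SAP names no CI method.

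**Worked case, n = 40 and p = 25%.** Ten isolates sit at each of 2, 4 and 8, with sum 20 + 40 + 80 = 140. Ten are off-scale.
- Coded 16: (140 + 160)/40 = 7.5
- Coded 32: (140 + 320)/40 = 11.5
- Coded 64: (140 + 640)/40 = 19.5
- Median: midpoint of the 20th and 21st values, (4 + 8)/2 = 6, under every coding
- SD: 5.4, 12.2 and 26.1
- Geometric mean, from mean log2 values of 100/40, 110/40 and 120/40: 5.7, 6.7 and 8.0

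**Other shares, n = 40** (entries are for coding 16 / 32 / 64):

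| Off-scale share | Mean | 95% CI for the mean | Median |
|---|---|---|---|
| 0% | 4.6 | 3.8–5.4 | 4 |
| 10% | 5.8 / 7.4 / 10.6 | 4.5–7.1 / 4.6–10.2 / 4.8–16.4 | 4 / 4 / 4 |
| 25% | 7.5 / 11.5 / 19.5 | 5.8–9.2 / 7.6–15.4 / 11.1–27.9 | 6 / 6 / 6 |
| 50% | 10.2 / 18.2 / 34.2 | 8.3–12.2 / 13.8–22.7 / 24.6–43.9 | 12 / 20 / 36 |

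From lowest to highest coding, the mean grows by a factor of 10.6/5.8 = 1.8 at 10%, 19.5/7.5 = 2.6 at 25% and 34.2/10.2 = 3.4 at 50%. With nothing off-scale, coding does not matter, and the mean (4.6) is only somewhat above the geometric mean (3.9).

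A larger sample does not help. If the 64 earlier Group 3 participants were pooled with these 40 (n = 104), the three intervals at 25% would be 6.5–8.5, 9.1–13.9 and 14.5–24.5, which do not overlap.

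Two limits on the alternatives also show. The median is stable only while fewer than half the isolates are off-scale, and the upper quartile moves earlier (10, 14 and 22 at 25%). Taking logs shrinks the dependence but does not remove it: at 50% the geometric mean is 7.9, 11.1 or 15.7.

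**The case against.** The best defence is that the mean is one item among several. The same paragraph gives median, IQR, minimum, maximum and a histogram, so a reader would see skew and a pile-up at the top. This stands, and it is why the point is modest. SAP 4.1 also limits means to where they are appropriate, but 4.3.2 lists the MIC mean and its CI without that condition. A coding rule may sit in the Analysis Implementation Plan, which is not among the documents. That is possible, although the comparable CFU and TTD rules are in the SAP itself.

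Three stronger readings are tempting, and the documents do not support them.
- A reader might infer that off-scale isolates are entered as 16. The figure of at least 16 is background on katG strains. No section gives this trial's assay range, says that results are reported that way, or says how they are coded.
- A reader might infer that the mean distorts the AUC/MIC analysis or the simulation. It enters neither. AUC/MIC uses each participant's own MIC (Protocol 10.2.1). The simulation uses the MIC distribution, mainly that of Group 1, with Group 3 exploratory (Protocol 9.6.2.3). The SAP leaves both to a separate PK plan. Off-scale values would need a rule there too, but changing SAP 4.3.2 would not supply it.
- A reader might take MIC description to be all that Step 1 is for. Protocol 9.1 also uses Step 1 to determine Step 2 eligibility.

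**Conclusion.** The concern holds in a limited form. A CI for the arithmetic mean is a poor summary of Group 3 MICs on the protocol's own background figures, and the plan has no stated scale or limit rule for MIC. That the raw scale is meant is inferred from the absence of any transformation.

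The numerical size is conditional. In the scenarios above, the mean moves by a factor of about 1.8 to 3.4 when 10% to 50% of isolates are off-scale, and not at all when none are. The off-scale share, the coding values and the on-scale pattern are all assumptions.

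No test or decision rests on this outcome. The report on Groups 1 and 2 and the earlier Group 3 Step 1 participants was complete in September 2018 (SAP 5), so the change concerns the second report. It is worth making, but it is of modest importance.

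**What to change.** For the Version 3.0 Group 3 report, and for any Version 2.0 MIC summaries carried into it for context:

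1. Drop the CI for the arithmetic mean MIC.
2. Report counts by dilution, with the number of isolates above the top concentration as its own category, and a cumulative percent-inhibited plot.
3. Report MIC50 and MIC90, shown as above the top concentration where they fall there.
4. Give a log2-scale geometric mean with 95% CI only where few or no isolates are off-scale. Otherwise take it from a censored fit labelled as a sensitivity analysis, because a single lognormal curve may not suit a distribution that the SAP itself suspects is bimodal.
5. State the tested concentration range.
6. In the separate PK plan, treat AUC/MIC for an off-scale isolate as an upper bound, since an MIC above the top concentration means that AUC/MIC lies below AUC divided by that concentration.

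The cost is low but not nil: the tested range has to be obtained from the laboratory, and slightly more programming is needed. No additional samples are needed.

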## 5 Report components

Detailed descriptions of the content of each of the following sections are given in the AIP.

1. Recruitment/Accrual
2. Participants and Data Ineligible for Analysis
3. Baseline Characteristics
4. Completeness of Database
5. Study Status
6. Treatment Status
7. Safety
  - Signs and Symptoms and Laboratory Abnormalities
  - Diagnoses
8. Primary Outcomes
9. Secondary Outcomes

Analyses of Group 1 and Group 2 Step 1 and Step 2 and Group 3 Step 1 participants enrolled under Protocol Version 2.0 were complete in 2018. Protocol Version 2.0 did not randomize Group 3 participants to receive any study treatment. Protocol Version 3.0 randomized Group 3 participants who met Step 1 and Step 2 entry criteria to receive 7 days of INH randomized 1:1 to one of two doses: 15 mg/kg or 20 mg/kg. As a result, there will be two separate primary statistical reports for this study:

1. A report Groups 1 and 2 Steps 1 and 2 and Group 3 Step 1 enrolled under Protocol Version 2.0 (complete and dated September 17, 2018)
2. A report covering Group 3 participants enrolled under Protocol version 3.0.

Note: some basic summaries from participants enrolled under Protocol Version 2.0 may also be included in the second report to provide context.
